4.3 Screen failures

Screen failures are defined as participants who consent to participate in the clinical study but who are not subsequently entered in the study/included in the analysis population. A minimal set of screen failure information is required to ensure transparent reporting of screen failure participants, to meet the Consolidated Standards of Reporting Trials (CONSORT) publishing requirements, as applicable, and to respond to queries from regulatory authorities. Minimal information includes date of consent, demography, screen failure details, eligibility criteria, and any serious AEs.

5 TREATMENTS

5.1 Study treatments

An investigational product, also known as investigational medicinal product in some regions, is defined a pharmaceutical form of an active substance being tested or used as a reference in a clinical study, including products already with a marketing authorization but used or assembled (formulated or packaged) differently than the authorized form, or used for an unauthorized indication, or when used to gain further information about the authorized form.

Investigational products used in this trial are:

- TMZ
- Nivolumab, solution for injection
- Ipilimumab, solution for injection

TMZ will be used in commercially available formulation. Refer to prescribing information for details of the formulation as well as packaging and handling requirements. TMZ hard capsules (20 mg, 100 mg, and 250 mg) should be administered in the fasting state. The capsules must be swallowed whole with a glass of water and must not be opened or chewed.

Nivolumab (BMS-936558-01) will be with a potency of 100mg (10 mg/ml) and 40 mg (10 mg/mL).

Ipilimumab (BMS-734016) will be with a potency of 200 mg (5 mg/mL).

5.2 Treatment Administration

In the lead-in treatment phase, patients will be treated with:

> TMZ: 150 mg/sqm daily on days 1-5 every 4 weeks, for two cycles.

At the end of the first treatment phase, patients will undergo a CT scan at week 8 +/- 5 days, based on which:

- Patients with PD according to RECIST v1.1 will be out of study.
- Twenty-seven patients with RECIST v1.1 CR/PR/SD will be evaluable in the ITT population and will enter the second treatment phase, being treated with the following NIVO+IPI+TMZ combination regimen:
 - NIVO: 480 mg i.v. every 4 weeks.
 - > IPI: 1 mg/Kg i.v. every 8 weeks.
 - TMZ: 150 mg/sqm daily on days 1-5, every 4 weeks.

Treatment will continue until confirmed disease progression, unacceptable toxicity, withdrawal of consent or death, whichever occurs first.

- In case of unacceptable toxicity unequivocally due to TMZ, NIVO and IPI can be continued until disease progression, or to unacceptable toxicity, informed consent withdrawal or death.
- In case of unacceptable toxicity unequivocally due to NIVO and/or IPI, single-agent TMZ can be continued until disease progression, or to unacceptable toxicity, informed consent withdrawal or death.

5.3 Dosage Modification

5.3.1 Dose Delay Criteria

Reasons for dose modifications or delays, the supportive measures taken, and the outcome will be documented in the patient's chart and recorded in the eCRF.

For toxicities which are considered by the investigator unlikely to develop into serious or life-threatening events (e.g. alopecia, altered taste etc.), treatment will be continued at the same dose without reduction or interruption. In addition, no dose reductions or interruptions will be required for anemia (non-hemolytic) as it can be satisfactorily managed by transfusions or erythropoietin. Where several toxicities with different grades or severity occur at the same time, the dose modifications applied should be the greatest reduction applicable.

If, in the opinion of the Investigator, a toxicity is considered to be due solely to one drug (e.g. immune-related adverse events related to IPI and/or NIVO), the dose of the other drugs does not require modification.

If a delay related to a study drug alone is required, the whole study treatment should be delayed as well until the requirements for restarting the therapy are met.

Dose modifications for isolated abnormal hematologic lab values will be based on hematological parameters at start of a treatment cycle.

Nivolumab or ipilimumab administration should be delayed for the following:

- Grade 2 non-skin, drug-related adverse event, with the exception of fatigue
- Grade 2 drug-related creatinine, AST, ALT, and/or Total Bilirubin abnormalities
- Grade 3 skin, drug-related adverse event
- Grade 3 drug-related laboratory abnormality, with the following exceptions: Grade 3 lymphopenia or asymptomatic amylase or lipase does not require dose delay Grade ≥ 3 AST, ALT, Total Bilirubin will require dose discontinuation (see Section 6.1)
- Any adverse event, laboratory abnormality, or intercurrent illness which, in the judgment of the investigator, warrants delaying the dose of study medication.

Participants who require delay of nivolumab/ipilimumab should be re-evaluated weekly or more frequently if clinically indicated and resume nivolumab/ipilimumab dosing when re-treatment criteria are met.

In case of unacceptable toxicity unequivocally due to TMZ, NIVO and IPI can be continued until disease progression, or to unacceptable toxicity, informed consent withdrawal or death.

In case of unacceptable toxicity unequivocally due to NIVO and/or IPI, single-agent TMZ can be continued until disease progression, or to unacceptable toxicity, informed consent withdrawal or death.

5.3.2 Criteria to Resume Treatment with Nivolumab and/or Ipilimumab

Participants may resume treatment with study drug when the drug-related AE(s) resolve to Grade ≤ 1 or baseline value, with the following exceptions:

- Participants may resume treatment in the presence of Grade 2 fatigue
- Participants who have not experienced a Grade 3 drug-related skin AE may resume treatment in the presence of Grade 2 skin toxicity
- For participants with Grade 2 AST, ALT, or Total Bilirubin elevations, dosing may resume when laboratory values return to baseline and management with corticosteroids, if needed, is complete.
- Drug-related pulmonary toxicity, diarrhea or colitis must have resolved to baseline before treatment is resumed. Participants with persistent Grade 1 pneumonitis after completion of a steroid taper over at least 1 month may be eligible for retreatment if discussed with and approved by Sponsor.
- Participants with drug-related endocrinopathies adequately controlled with only physiologic hormone replacement may resume treatment after consultation with the Sponsor Medical Monitor (ordesignee). Adrenal insufficiency requires discontinuation regardless of control with hormone replacement

5.3.3 Treatment of Nivolumab- or Ipilimumab-related Infusion Reactions

Since nivolumab and ipilimumab contain only human immunoglobulin protein sequences, they are unlikely to be immunogenic and induce infusion or hypersensitivity reactions. However, if such a reaction were to occur, it might manifest with fever, chills, rigors, headache, rash, pruritus, arthralgias, hypotension, hypertension, bronchospasm, or other allergic-like reactions. All Grade 3 or 4 infusion reactions should be reported within 24 hours to the study medical monitor/designee and reported as an SAE if it meets the criteria. Infusion reactions should be graded according to NCI CTCAE (current version) guidelines. Treatment recommendations are provided below and may be modified based on local treatment standards and guidelines, as appropriate.

For **Grade 1** symptoms (mild reaction; infusion interruption not indicated; intervention not indicated):

Remain at bedside and monitor participant until recovery from symptoms. The following prophylactic
premedications are recommended for future infusions: diphenhydramine 50 mg (or equivalent) and/or
acetaminophen/paracetamol 325 to 1000 mg at least 30 minutes before additional nivolumab
administrations.

For **Grade 2** symptoms: (moderate reaction required therapy or infusion interruption but responds promptly to symptomatic treatment (e.g., antihistamines, non-steroidal anti-inflammatory drugs, narcotics, corticosteroids, bronchodilators, IV fluids); prophylactic medications indicated for ≤ 24 hours):

- Stop the study drug infusion, begin an IV infusion of normal saline, and treat the participant with diphenhydramine 50 mg IV (or equivalent) and/or acetaminophen/paracetamol 325 to 1000 mg; remain at bedside and monitor participant until resolution of symptoms. Corticosteroid and/or bronchodilator therapy may also be administered as appropriate. If the infusion is interrupted, then restart the infusion at 50% of the original infusion rate when symptoms resolve; if no further complications ensue after 30 minutes, the rate may be increased to 100% of the original infusion rate. Monitor participant closely. If symptoms recur, then no further study medication will be administered at that visit.
- For future infusions, the following prophylactic premedications are recommended: diphenhydramine 50 mg (or equivalent) and/or acetaminophen/paracetamol 325 to 1000 mg should be administered at least 30 minutes before nivolumab and/or ipilimumab infusions. If necessary, corticosteroids (up to 25 mg of hydrocortisone or equivalent) may be used.

For **Grade 3 or 4** symptoms: (severe reaction, Grade 3: prolonged [i.e., not rapidly responsive to symptomatic medication and/or brief interruption of infusion]; recurrence of symptoms following initial improvement; hospitalization indicated for other clinical sequelae (e.g., renal impairment, pulmonary infiltrates). Grade 4: Life threatening; pressor or ventilatory support indicated):

• Immediately discontinue infusion of study drug. Begin an IV infusion of normal saline and treat the participant as follows: Recommend bronchodilators, epinephrine 0.2 to 1 mg of a 1:1000 solution for subcutaneous administration or 0.1 to 0.25 mg of a 1:10,000 solution injected slowly for IV administration, and/or diphenhydramine 50 mg IV with methylprednisolone 100 mg IV (or equivalent), as needed. Participant should be monitored until the Investigator is comfortable that the symptoms will not recur. Study drug will be permanently discontinued. Investigators should follow their institutional guidelines for the treatment of anaphylaxis. Remain at bedside and monitor participant until recovery of the symptoms.

In case of late-occurring hypersensitivity symptoms (e.g., appearance of a localized or generalized pruritus within 1 week after treatment), symptomatic treatment may be given (e.g., oral antihistamine or corticosteroids).

5.3.4 Management Algorithms for Immuno-Oncology Agents

Details on immune related adverse event management algorithm can be found in Appendix VIII for the following categories:

- GI Adverse Event
- Renal Adverse Event
- Pulmonary Adverse Event
- Hepatic Adverse Event
- Endocrinopathy Management
- Skin Adverse Event
- Neurological Adverse Event

5.3.5 Dose Reductions for TMZ

Dose modifications criteria for TMZ-related adverse events are listed below:

TMZ dose levels					
Dose level	TMZ dose (mg/mq/day)	Remarks			
0	150	Dose during Cycle 1			
- 1	113	Due to prior toxicity			
- 2	75	Due to prior toxicity			
TMZ dose reduction					
Toxicity	Reduce TMZ by 1 dose level	Discontinue TMZ			
Absolute neutrophil count	<1.0 x 10 ⁹ /l	If dose level -1 still results in			
Thrombocyte count	<50 x 10 ⁹ /l	unacceptable toxicity			
CTC non-hematological Toxicity	CTC grade 3	CTC grade 4			
(except for alopecia, nausea,					
vomiting)					

For dose calculations, please refer to the following Table:

25% dose reduction = 113 mg/m / m ² /day		N. of 250 mg tablets at each dose	N. of 100 mg tablets at each dose	N. of 20 mg tablets at each dose
Surface Area (m ²)	Total Daily Dose (mg) *	Morning	Morning	Morning
≤ 1.37	160	-	1	3
1.38 – 1.62	180	-	1	4
1.63 - 1.87	200	-	2	-
≥ 1.88	220	-	2	1
	50% dose reduction 75 mg/m / m ² / day		N. of 100 mg tablets at each dose	N. of 20 mg tablets at each dose
Surface Area (m ²)	Total Daily	Morning	Morning	Morning
	Dose (mg) *			
≤ 1.37	100	-	1	-
1.38 – 1.62	120	-	1	1
1.63 - 1.87	140	-	1	2
≥ 1.88	160	-	1	3

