
participants treated with nivolumab monotherapy and nivolumab and ipilimumab combination therapy are listed in the current version of the nivolumab IB (53).

TMZ

In patients treated with TMZ, whether used in combination with RT or as monotherapy following RT for newly-diagnosed glioblastoma multiforme, or as monotherapy in patients with recurrent or progressive glioma, the reported very common adverse reactions were similar: nausea, vomiting, constipation, anorexia, headache and fatigue. Convulsions were reported very commonly in the newly-diagnosed glioblastoma multiforme patients receiving monotherapy, and rash was reported very commonly in newly-diagnosed glioblastoma multiforme patients receiving TMZ concurrent with RT and also as monotherapy, and commonly in recurrent glioma. Most hematological adverse reactions were reported commonly or very commonly in both indications.

Newly-diagnosed glioblastoma multiforme

Myelosuppression (neutropenia and thrombocytopenia), which is a known dose-limiting toxicity for most cytotoxic agents, including TMZ, was observed. When laboratory abnormalities and adverse events were combined across concomitant and monotherapy treatment phases, Grade 3 or Grade 4 neutrophil abnormalities including neutropenic events were observed in 8 % of the patients. Grade 3 or Grade 4 thrombocyte abnormalities, including thrombocytopenic events were observed in 14 % of the patients who received TMZ.

Recurrent or progressive malignant glioma

In clinical trials, the most frequently occurring treatment-related undesirable effects were gastrointestinal disorders, specifically nausea (43 %) and vomiting (36 %). These reactions were usually Grade 1 or 2 (0 – 5 episodes of vomiting in 24 hours) and were either self-limiting or readily controlled with standard anti- emetic therapy. The incidence of severe nausea and vomiting was 4 %.

Grade 3 or 4 thrombocytopenia and neutropenia occurred in 19 % and 17 % respectively, of patients treated for malignant glioma. This led to hospitalization and/or discontinuation of TMZ in 8 % and 4 %, respectively. Myelosuppression was predictable (usually within the first few cycles, with the nadir between Day 21 and Day 28), and recovery was rapid, usually within 1-2 weeks. No evidence of cumulative myelosuppression was observed. The presence of thrombocytopenia may increase the risk of bleeding, and the presence of neutropenia or leukopenia may increase the risk of infection.

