In a population pharmacokinetics analysis of clinical trial experience there were 101 female and 169 male subjects for whom nadir neutrophil counts were available and 110 female and 174 male subjects for whom nadir platelet counts were available. There were higher rates of Grade 4 neutropenia (ANC < 0.5 x 109 /l), 12 % vs 5 %, and thrombocytopenia (< 20 x 109 /l), 9 % vs 3 %, in women vs men in the first cycle of therapy. In a 400 subject recurrent glioma data set, Grade 4 neutropenia occurred in 8 % of female vs 4 % of male subjects and Grade 4 thrombocytopenia in 8 % of female vs 3 % of male subjects in the first cycle of therapy. In a study of 288 subjects with newly-diagnosed glioblastoma multiforme, Grade 4 neutropenia occurred in 3 % of female vs 0 % of male subjects and Grade 4 thrombocytopenia in 1 % of female vs 0 % ofmale subjects in the first cycle of therapy.

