- ^c Required follow-up information will be collected via telephone calls and/or clinic visits every 3 months until death, withdrawal of consent, the patient is lost to follow-up, or study termination, whichever occurs first.
- ^d Informed consent must be documented before any study-specific screening procedure is performed and may be obtained up to 28 days before initiation of study treatment.
- ^e Archival tumor tissue for centralized molecular screening will be obtained up to 28 days before initiation of study treatment. Note: A separate tissue screening informed consent form may be used to obtain consent to send the sample to the central laboratory. Subjects may continue on prior therapy while tissue testing takes place (see Section 7.10).
- f Includes respiratory rate, heart rate, temperature, blood oxygen saturation and systolic and diastolic blood pressure while the patient is in a seated position. Any abnormality identified at baseline prior to the first treatment phase should be recorded on the General Medical History and Baseline Conditions eCRF. At subsequent visits record new or worsened clinically significant abnormalities on the Adverse Event eCRF.
- g Vital signs at the first NIVO and IPI infusion will be collected within 60 min prior to the infusion and 30 (± 10) minutes after the infusion. During the infusion, the patient's vital signs will be determined only in presence of distress/infusion-related reactions. For subsequent infusions, vital signs will be collected within 60 minutes before infusion and at the end of the infusion.
- ^h Hematology includes CBC, hemoglobin, hematocrit, WBC count with differential [neutrophils, eosinophils, lymphocytes], and platelet count. Hematology will be collected ≤ 48 hours prior to every treatment administration.
- ⁱ Coagulation includes INR, aPTT. Coagulation will be collected at screening and before every optional biopsy.
- j Serum chemistry includes: glucose, BUN or urea, creatinine, sodium, potassium, calcium, total bilirubin, direct bilirubin, ALT, AST, ALP, LDH, lipase, amylase, and LDH. Serum chemistry will be collected ≤ 48 hours prior to every treatment administration.
- ^k CEA will be done at screening and every 8 weeks (± 1 week) until disease progression leading to treatment discontinuation. After 12 months of treatment, it will be performed every 12 weeks.

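### When TMZ is given alone, the only written action for low start-of-cycle counts is a one-level dose reduction; delay is left to judgement and no TMZ restart count is defined

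*Protocol*

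**What the plan says.** The table in Section 5.3.5 has two action columns. For ANC <1.0 or thrombocytes <50 x 10^9/l the first reads "Reduce TMZ by 1 dose level". The second, discontinuation, applies "If dose level -1 still results in" unacceptable toxicity. Three dose levels are defined: 150, 113 and 75 mg/m2 per day. The last, level -2, has its own dosing table.

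Section 5.3.1 fixes which counts are used: "Dose modifications for isolated abnormal hematologic lab values will be based on hematological parameters at start of a treatment cycle". Appendix I adds "Hematology will be collected ≤ 48 hours prior to every treatment administration".

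The delay list in 5.3.1 opens with "Nivolumab or ipilimumab administration should be delayed for the following", and Section 5.3.2 is headed "Criteria to Resume Treatment with Nivolumab and/or Ipilimumab". Section 5.3.1 also has a general sentence: if one study drug has to be delayed, all study treatment waits until the restart conditions are met.

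On TMZ myelosuppression, Section 1.4.3.1 describes a predictable course, "with the nadir between Day 21 and Day 28), and recovery was rapid, usually within 1-2 weeks".

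**The concern.** In the lead-in, TMZ is given on Days 1 to 5 of a 28-day cycle, for two cycles. Nivolumab and ipilimumab have not started, so the delay triggers and resume criteria written for them have nothing to act on. The same is true later if TMZ continues alone after NIVO/IPI toxicity. In both settings a site that finds counts below the table limits has one written action: a lower dose. The protocol gives no count at which TMZ should be held and none at which it may restart.

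What is at stake is patient safety. Section 1.4.3.1 links thrombocytopenia to bleeding and neutropenia or leukopenia to infection, and Section 5.6.2 strongly discourages starting or increasing colony-stimulating factors. A one-level reduction does not prevent dosing on unrecovered counts; a hold does. Sites may also handle the same count differently, because each has to supply its own restart rule.

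**Working it through.** The protocol states no figure to reproduce here. The check is date arithmetic plus a comparison of the relevant sections.

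**Timing**
- Cycle length is 28 days (Section 5.2, Appendix I), so Cycle 2 Day 1 = 1 + 28 = Day 29.
- The nadir is at Day 21 to 28, with recovery 7 to 14 days later (Section 1.4.3.1). Earliest recovery is 21 + 7 = Day 28; latest is 28 + 14 = Day 42.
- Day 29 is therefore 29 - 28 = 1 day to 29 - 21 = 8 days after the nadir, at the very start of the recovery range.
- Appendix I lets TMZ move by 3 days either way, so Day 26 to Day 32. The early end lies inside the nadir window. The late end is 42 - 32 = 10 days before the latest recovery.

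**Dose under the written action**
- One level down is 113 mg/m2 per day: 113/150 = 75% of the full dose.
- Over five days this is 5 x 113 = 565 mg/m2, against 5 x 150 = 750 mg/m2.
- The count rows have no lower cut-off, so a far lower count gets the same instruction. For non-haematological toxicity, by contrast, the table separates Grade 3 (reduce) from Grade 4 (discontinue).

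**Which rules reach which setting**

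| Rule | Lead-in Cycle 2, or TMZ alone | Combination phase |
|---|---|---|
| 5.3.5 table | Applies: reduce or discontinue | Applies |
| 5.3.1 delay list | Headed for NIVO/IPI | A Grade 3 drug-related laboratory abnormality delays NIVO/IPI |
| 5.3.1 general delay sentence | Wording covers any study drug, but no TMZ restart condition is defined | Extends a NIVO/IPI delay to all treatment |
| 5.3.2 resume criteria | Headed for NIVO/IPI | Grade 1 or less, or baseline |

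In the combination phase, to the extent that the low count grades as a Grade 3 drug-related abnormality, a hold and a restart rule exist. In the left-hand column they do not. The ANC 1.5 and platelet 100 x 10^9/l limits in Section 4.2 are entry criteria only.

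**Can the number affected be computed?** Section 1.4.3.1 reports first-cycle Grade 4 rates, women against men, including "higher rates of Grade 4 neutropenia (ANC < 0.5 x 109 /l), 12 % vs 5" percent. Across its three data sets the neutropenia rates are 12 vs 5%, 8 vs 4% and 3 vs 0%. Applied to about 100 lead-in patients (Section 4):
- highest rates, half women: 100 x (0.5 x 0.12 + 0.5 x 0.05) = 8.5;
- lowest rates, women in the proportion 101/270: 100 x (101/270) x 0.03 = 1.1.

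These results do not count the patients affected. They describe nadir counts below 0.5, whereas the rule uses start-of-cycle counts below 1.0. Reading the nadir instead of Day 29 overstates; leaving out counts from 0.5 to 1.0 understates. The direction of the net error is unknown. The two data sets whose disease is named are glioma, and no dose is given.

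**Level -1 against level -2.** A second low count at level -1 meets the first column (go to 75 mg/m2) and, if judged unacceptable, the second column (stop). No haematological action is given for a patient already at level -2.

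**The case against.** The strongest reply is that the protocol does not forbid a delay. The general delay sentence in 5.3.1 covers any study drug. The last item in its delay list, although under the NIVO/IPI heading, speaks generally of abnormalities that the investigator judges to warrant delaying study medication. Section 7 sends immediate safety concerns to the sponsor, and Section 6.1 requires stopping for any condition that endangers the patient. The 5.3.5 table can also be read as setting the level after toxicity, since its lower levels are marked as due to prior toxicity, without ordering a dose that day.

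This stands in part. A reader might infer that the protocol orders same-day dosing on unrecovered counts, or leaves no way to hold TMZ. The documents do not support that: delay is possible, but it rests on judgement. What remains is that no restart condition for TMZ is written, the scheduling window is only 3 days, and Section 7 rules out protocol waivers.

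A reader might also infer a patient count from the Grade 4 rates, or extend the concern to every combination cycle. Neither follows, for the reasons shown in the working. Section 1.4.3.1 further reports no evidence of cumulative myelosuppression.

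Finally, it might seem natural to adopt the entry limits of ANC 1.5 and platelets 100 x 10^9/l for every cycle. That goes beyond the gap: it would also hold patients with ANC 1.0 to 1.49 or platelets 50 to 99, whom the table now doses without reduction.

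On the level -1 point, unacceptable toxicity is a reason to stop at any level, and level -2 can be reached through Grade 3 non-haematological toxicity. The conflict is therefore minor, but the haematological rows remain unclear.

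**Conclusion.** The point holds for TMZ given alone: lead-in Cycle 2 Day 1, and TMZ continued after NIVO/IPI toxicity. There, the only written action for a start-of-cycle ANC <1.0 or thrombocytes <50 x 10^9/l is a one-level reduction, with discontinuation if level -1 still gives unacceptable toxicity. By the protocol's own description of the nadir, Day 29 comes when recovery is only beginning.

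The conclusion rests on the stated nadir and recovery times applying to this population, and on reading the headings of the delay list and of 5.3.2 as limiting their scope. The number of patients affected is unknown. Sample size, alpha and power do not change. This is a dosing-safety gap that should be closed; it is not a flaw in the statistical design. The clash between the level -1 stop rule and level -2 is a separate, smaller drafting conflict.

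**What to change.** Add to Section 5.3.5: *If ANC is <1.0 or thrombocytes <50 x 10^9/l at the start of a cycle, hold TMZ, repeat counts weekly, and resume one dose level lower once counts recover to Grade 1 or less or baseline.* The restart condition is the one already in 5.3.2, so no second standard is created.

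Change the stop cell so that discontinuation follows unacceptable toxicity at level -2, or delete level -2. Deleting it also removes the second step down for Grade 3 non-haematological toxicity, so moving the stop rule is the cleaner choice.

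The drafting cost is one paragraph and one table cell in an amendment. The other costs are:
- Held patients need extra weekly blood counts.
- Cycle 2 may come late relative to the lead-in scan that decides entry to the combination phase. A two-week hold moves Cycle 2 Day 1 to 29 + 14 = Day 43. A scan at week 7 (7 x 7 = Day 49, Section 3.1.1) then follows 6 days later, instead of 49 - 29 = 20. Section 5.2 gives week 8, which leaves 56 - 43 = 13 days. Section 7.6.1 keeps scans independent of dose delay, so the scan should stay where it is and the actual Cycle 2 start should be recorded.
- In the combination phase, a TMZ hold also delays NIVO and IPI under 5.3.1.
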